Veterans will be considered 'actively engaged in psychotherapy in our study' when their study therapist has not officially closed their therapy case. Cases are closed when the veteran has completed their course of PE, when the veteran tells their therapist they have quit PE, or when providers have exhausted outreach attempts to a veteran who has missed a scheduled session(s). SPs in the PE2 condition are considered 'actively engaged in psychotherapy in our study' when their veteran is actively engaged in psychotherapy in our study. SPs in the Standard PE condition are never considered 'actively engaged in psychotherapy in our study.'

Managing risk from CBOCs and in-home video telehealth sessions. Due to the nature and distance between the Veteran and telemental health provider incurred in telemedicine practice, additional measures will be taken to ensure patient safety. These procedures will be in place during all telemedicine sessions:

- a. Study providers will follow the guidelines detailed in the 2017 Department of Veteran Affairs National Telemental Health Supplement and the 2012 Telemental Health Suicide Prevention and Emergency Care manual.
- b. Providers will use VA approved electronic communication methods
- c. All study providers will follow their site's local telemental health policies and emergency procedures at each facility and clinic.
- d. Providers will always adhere to established face-to-face assessment protocols.
- e. Telemental health provider will have detailed contact information from the patient with particular attention to who could be contacted in the event of an emergency. All emergency contact information, local police phone numbers and local emergency room contact information should be readily retrievable during all sessions.
- f. Providers will use the National Telehealth Help Desk when necessary: [name].

Additional manners to manage risk from CBOCs.

- a. For all telemental health sessions at CBOC locations, a CBOC staff person will be available to assist Veteran should the need arise.
- b. CBOC staff will be available by telephone for the remote telemedicine study provider should they need to emergently contact an on-site VA staff.
- c. If a patient becomes suicidal, homicidal, psychotic, or agitated, the Telehealth provider will ask for assistance from the CBOC staff who would help in deescalating the patient and/or initiating commitment.

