3. Have a SP (intimate partner, family member, or friend) with contact at least 3 times a week	Self-report item	8. Severe substance use problem in past 3 months	SCID-5-CT ¹²
4. Will allow a SP to participate	Self-report item	9. Moderate relationship violence	IPSVS Adapted ¹⁰⁸
5. Willing to be seen via telehealth when in-person treatment options aren't available.		10. Veteran has underlying medical condition or a planned medical procedure likely to impair ability to engage in treatment.	
		11. SP screens positive for PTSD	PCL-5
		12. Veteran and/or SP fails to complete baseline survey	

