6.0 Reporting

We will follow the VA Central IRB Table of Reporting Requirements for all issues that must be reported (i.e. summary of adverse events, unexpected problems and any actions or changes with respect to the protocol).

Adverse events (AE) include any untoward medical occurrence in a patient or clinical investigation subject administered an intervention and which does not necessarily have a causal relationship with this treatment. We will collect the following safety information (adverse events) that occurred within 7 days leading up to the final assessment.

1. Suicide attempts
2. Hospitalizations for mental health
3. Episodes of family violence

Therapists will be instructed to notify study staff immediately when such events occur during treatment delivery. Staff will report directly to the local site PI regarding any events. Counselors will also meet regularly by phone for case consultation with a study investigator, where the occurrence of any of these events will be further discussed and tracked. Questions regarding the occurrence of each of these three events will be included in posttreatment assessments. Data obtained from participants will be reviewed for safety concerns. In the case of problems, the staff will discuss this with the appropriate site PI.

Of note, survey reports of IPV on posttreatment and follow-up surveys will be reported when respondents endorse items consistent with severe violence. This includes the following: (1) hit my partner with a fist or something hard, (2) kicked my partner, (3) slammed my partner against something, (4) beat my partner, (5) burned my partner on purpose, (6) tried to hurt my partner by choking or suffocating him/her, or (7) used a knife or gun on my partner. Examples of serious adverse effects, according to the FDA, include death, life-threatening adverse events, suicide attempts, and hospitalization. Consequently, endorsement of items 6 or 7 will be considered a SAE. Given the population, some incidents of severe IPV are expected. Reports of severe IPV on baseline surveys are part of our exclusionary criteria (see inclusions/exclusions). Thus, severe IPV in reported in baseline surveys will not be reported as adverse events.

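### Section 6.0 sets two severity thresholds for family violence, and a non-severe episode that a support person reports during treatment has a planned path into the adverse event tally only in the family arm

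*Combined protocol and SAP*

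**What the plan says.** Section 6.0 (Reporting) names three adverse events. The third is "Episodes of family violence", with no severity grade and no limit to intimate partners. Three routes can bring such an event to the study.

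- Therapists: "Therapists will be instructed to notify study staff immediately when such events occur during treatment delivery".
- Direct questions: "Questions regarding the occurrence of each of these three events will be included in posttreatment assessments". No severity limit or arm restriction is given, and the respondent (Veteran, SP or both) is not named.
- Survey items on intimate partner violence (IPV): "survey reports of IPV on posttreatment and follow-up surveys will be reported when respondents endorse items consistent with severe violence". Seven severe acts follow, each worded as something the respondent did to a partner. Two of them count as serious adverse events.

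The same section gives a collection window: "We will collect the following safety information (adverse events) that occurred within 7 days leading up to the final assessment".

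Section 5.1K.1 (IPV reports on surveys) adds that baseline, weekly and posttreatment surveys ask about IPV, and that study providers review these answers while the respondent is actively engaged in study psychotherapy. SPs in family supported PE have that status while their Veteran does. By contrast, "SPs in the Standard PE condition are never considered 'actively engaged in psychotherapy in our study". Section 6.0 has no reporting rule for weekly survey answers.

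**The concern.** One kind of event is held to two thresholds, and no sentence says which governs. A shove that a therapist hears about is an adverse event under the list. The same shove endorsed only on a posttreatment survey is not reported.

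This would be untidy but harmless if every participant had the same access to each route. They do not. The therapist route carries the wider definition, and family-arm SPs are given planned access to it that standard-arm SPs lack.

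Violence between Veteran and SP is a harm of direct interest when SPs are brought into treatment. Section 5.1J.1 itself warns that having the pair discuss their relationship could change it. Non-severe episodes are plausible, because section 5.3 defines the violence exclusion by severe episodes in the past year. A tally whose ascertainment depends on arm could suggest harm in the family arm where there is none, or blur a real difference in non-severe violence.

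**Working it through.** The documents give no adverse event rate or count, so there is no figure to reproduce. The check is a comparison of the passages, followed by a sensitivity illustration.

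**Step 1. Access to each route**

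| Route | Threshold | Veteran (both arms) | SP, family arm | SP, standard arm |
|---|---|---|---|---|
| Therapist notification during treatment (6.0) | none stated | yes, through sessions | planned: sessions 1, 2a and 2b, two calls, added dyadic sessions if needed (5.1D) | not planned; possible if the SP contacts the provider, expected to be rare (5.1C) |
| Provider review of IPV survey answers, which can feed the therapist route (5.1K.1) | none stated | while in treatment | while the Veteran is in treatment | never |
| Direct posttreatment questions (6.0) | none stated | respondent not named; no arm restriction | same | same |
| Posttreatment and follow-up survey items (6.0) | severe only | yes | yes | yes |

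The therapist and provider-review rows differ by arm for SPs. Both carry the wider threshold. The two rows that are the same in both arms are the posttreatment questions, which may be limited by the 7-day window, and the severe-only survey rule.

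**Step 2. How much this could matter, under assumptions**

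The number per arm, 78 dyads, is from section 5.1. Everything else is assumed:

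- r = share of dyads with a non-severe episode, equal in both arms: 10% to 20%
- pV = chance that the therapist learns of it from the Veteran, both arms: 20% to 40%
- pS = chance that the therapist learns of it from the SP, family arm only: 20% to 40%
- q = chance that the direct posttreatment questions record it, equal in both arms: 0, 50% or 100%
- disclosures are independent

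Counted, standard = 78 × r × [1 − (1 − pV)(1 − q)]

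Counted, family = 78 × r × [1 − (1 − pV)(1 − pS)(1 − q)]

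Artificial excess = 78 × r × (1 − pV) × pS × (1 − q)

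The ratio does not depend on r.

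- q = 0: lowest ratio at pV = 0.4, pS = 0.2, which is 0.52 / 0.40 = 1.3. Highest at pV = 0.2, pS = 0.4, which is 0.52 / 0.20 = 2.6. The excess runs from 78 × 0.1 × 0.6 × 0.2 = 0.9 to 78 × 0.2 × 0.8 × 0.4 = 5.0 events.
- q = 0.5: lowest 0.76 / 0.70 = 1.09, highest 0.76 / 0.60 = 1.27. The excess halves, to 0.5 to 2.5 events.
- q = 1: ratio 1.0, no excess.

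The direction follows from the text. The size turns on q, which the documents do not fix. If the 7-day window governs the direct questions, q is small for episodes earlier in treatment. If it does not, q could be large. Positive correlation between Veteran and SP disclosure would shrink the ratio further.

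**The case against.** The strongest reply is that the direct posttreatment questions already ask about family violence without a severity limit and without regard to arm. This stands in part: it narrows the imbalance, possibly to nothing. It does not remove the two thresholds, which then sit within the same assessment, and the stated window may exclude most of the treatment period.

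Second, the severe-only sentence governs what is reported, not what is collected. This stands. Milder survey answers should remain in the dataset, so only the adverse event tally is affected. It is also why the remedy is cheap.

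Third, no between-arm analysis of adverse events appears in section 5.6, and section 5.1M does not say that safety reports are split by arm. This also stands and limits the consequence.

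Three stronger readings are tempting and are not supported:

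- A reader might infer that the tally will overstate family-arm violence by 1.3 to 2.6 times, or that most non-severe episodes are counted nowhere. Those figures hold only if the posttreatment questions capture nothing.
- A reader might infer that standard-arm SP experience cannot reach the therapist at all. Section 5.1C allows SP-initiated contact, and the Veteran can report in either arm. What is missing is a planned SP route.
- A reader might infer from the partner wording that violence involving a parent, sibling or friend is missed, since Table 4 asks that the Veteran "Have a SP (intimate partner, family member, or friend) with contact at least 3 times a week". The survey is in separate materials, so its instructions and full item set cannot be seen, and section 5.3 applies the term IPV to any SP. This is a point to confirm, not a finding.

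**Conclusion.** The concern holds in a limited form. Section 6.0 applies two severity thresholds to one event. Read with sections 5.1K.1 and 5.1D, it gives a non-severe episode reported by an SP during treatment a planned path into the adverse event tally in the family arm only. The link from provider review of survey answers to therapist notification is an inference from joining the two sections; the documents do not spell it out.

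The effect is on safety tallies and reports to the Data and Safety Monitoring Board, not on session attendance or any planned efficacy analysis. Its size cannot be derived from the documents. The illustrated range, a ratio of 1.0 to 2.6 and an excess of 0 to about 5 events, rests wholly on assumed rates and shows only that the answer depends on an unstated detail of the posttreatment questions. The passages should be reconciled because the correction is cheap and removes an arm-dependent element from the record of a harm of direct interest.

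**What to change.** In section 6.0, reconcile the passages so that one definition applies to every route.

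1. Keep the present broad scope of family violence. Grade each episode severe or non-severe using the existing list of survey items, whatever the source.
2. Tabulate both grades by arm and by source: survey answer, direct posttreatment question, therapist report only.
3. Read any arm comparison from the survey answers that both arms complete: the weekly surveys at weeks 2, 4, 5, 6, 8, 10 and 12, posttreatment, and the 3-month follow-up. Show therapist-only reports separately.
4. State the time covered by each source. Under section 5.5A.2 the posttreatment survey falls at the final session, at 16 weeks for dropouts, and up to 24 weeks for late completers, so its timing follows attendance and may differ by arm. Say also whether the 7-day window applies to each route, and how weekly answers enter the table.
5. Confirm from the survey materials that the partner in the items means the enrolled SP whatever the relationship. If it does not, flag answers from non-partner dyads in the table.

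Expedited reporting, the serious adverse event rule and the handling of individual disclosures stay as they are. No survey item needs rewording, so answers already collected stay comparable. The cost is protocol wording, one more table, and a higher stated count of non-severe events.

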IPV reports on surveys. Baseline, weekly, and posttreatment surveys ask about intimate partner violence (IPV). IPV reports are not routinely considered psychiatric emergencies that warrant breaching participants' confidentiality. Additionally, reaching out to all those who endorse IPV may have unintended negative consequences. Reaching out when uninvited to ask IPV victims to further discuss their IPV may be distressing and bring up traumatic memories. The outreach may be unwelcome, perceived as intrusive, and discourage future reporting. Discussing violence over the phone may also place the victim at risk to be overheard by the abuser, other loved ones, or children in the home. Consequently, a list of resources will be included with baseline, posttreatment, and follow-up surveys, including for IPV. Letters accompanying surveys will encourage respondents to contact study staff if they would like to discuss any of their survey responses. We will rely on participants to contact study staff if they wish to discuss their IPV experiences further. If participants are excluded due to IPV, the staff member notifying the reporter of their exclusion will offer local and national resources for IPV.

When the IPV reporter is actively engaged in psychotherapy in our study (i.e., veterans who are actively participating in PE and loved ones are actively participating in PE2), the reporter has an ongoing relationship with their study provider. In this circumstance, the reporter has the

reasonable expectation that the provider is reviewing their surveys and may ask them more about it. Thus, when a participant is actively engaged in psychotherapy in our study, providers will review IPV survey responses and intervene as clinically indicated, keeping the safety of the reporter of paramount concern. Providers will not breach the reporter's confidentiality unless they have the reporter's verbal permission or are concerned they must do so to prevent imminent harm.

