Regarding relationship violence, when the veteran reports they have been the target of moderate violence from their SP, the study team, under the supervision of the local Site PI, will determine if the violence should be the immediate focus of clinical attention. That is, (1) is the reporter is in danger of harm and, therefore, the focus of clinical attention should be on safety, or (2) would the reporter prefer to focus on IPV rather than PTSD. Importantly, each Site PI is a licensed, clinical psychologist with the appropriate training and expertise to make these

decisions. If the violence should be the focus of immediate clinical attention, then the dyad will be deemed ineligible and provided appropriate referrals. If the violence should not be the focus of clinical attention (e.g., the reporter is not in danger and does not wish to focus on IPV) the reporter may select a different loved one with which to participate in the study.

The new SP will also be screened and subject to the same inclusion/exclusion criteria, including that the new SP cannot be ineligible due to moderate IPV towards the veteran. The original SP will be deemed ineligible. The details of the reason the initial SP was ineligible will not be disclosed. The reporting dyad member(s) will be provided with resources and referrals for IPV (see IPV risk algorithm). Ineligible dyads may be re-evaluated for eligibility when this exclusionary criteria has been resolved (i.e., one year has passed without an episode of severe violence or six months without minor violence).

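### Section 6.0's survey trigger for severe partner violence lists only acts the respondent committed, so violence received is left unclassified, most plainly at the 3-month follow-up survey

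*Combined protocol and SAP*

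**What the plan says.** Section 6.0 (Reporting) sets the rule for surveys: "survey reports of IPV on posttreatment and follow-up surveys will be reported when respondents endorse items consistent with severe violence". It then lists seven acts:

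- Items 1 to 3: "1) hit my partner with a fist or something hard, (2) kicked my partner, (3) slammed my partner against something".
- Items 4 and 5: "4) beat my partner, (5) burned my partner on purpose".
- Items 6 and 7: "6) tried to hurt my partner by choking or suffocating him/her, or (7) used a knife or gun on my partner".

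The general standard for seriousness comes next: "Examples of serious adverse effects, according to the FDA, include death, life-threatening adverse events, suicide attempts, and hospitalization". From it the section draws the survey rule: "Consequently, endorsement of items 6 or 7 will be considered a SAE".

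The same section has broader provisions. Family violence is one of three AE categories, collected for the 7 days before the final assessment. Therapists are to tell study staff at once of such events during treatment delivery. Posttreatment assessments will ask about all three categories. Participant data will be reviewed for safety concerns, and problems go to the site PI.

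Elsewhere the plan treats violence as running both ways. Section 5.1I.1 excludes dyads for moderate violence by either member, and section 5.3 takes reports from both. Section 5.3 also has a pathway for use "when the veteran reports they have been the target of moderate violence from their SP". Section 5.1K.1, on survey reports of intimate partner violence (IPV), is written with victims in mind: "Reaching out when uninvited to ask IPV victims to further discuss their IPV may be distressing". Section 5.5A.3 sends the 3-month follow-up survey to Veterans and SPs alike.

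**The concern.** The only explicit SAE rule for survey reports is tied by number to two items, and both describe something the respondent did. Followed to the letter, the rule is set off by the person who used the weapon and not by the person it was used on. Yet the plan expects survey answers from victims and does not say how those answers are classified once the trial is running.

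Two things are at stake. The first is completeness: events that section 6.0 groups with life-threatening ones feed the PI's report to the Central IRB, due within 5 business days, and the safety reporting to the DSMB under section 5.1M. The second is consistency: three sites reading the same list could classify the same victim's report differently. Section 5.1J.1 accepts that asking the dyad to discuss their relationship could alter it, so family violence is a safety outcome that this trial has reason to count carefully.

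**Working it through.** No arithmetic in the plan bears on this point, so the check is a reading of the text.

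**1. Direction of the listed items.**

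| Items in section 6.0 | Worded as committed | Worded as received |
|---|---|---|
| 1 to 7 (reportable) | 7 of 7 | 0 of 7 |
| 6 and 7 (SAE) | 2 of 2 | 0 of 2 |

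**2. A test case.** Suppose that a Veteran chokes the SP after treatment ends, and both complete the 3-month survey. If the Veteran endorses item 6, the rule makes it an SAE. If only the SP reports it, as something done to them, no listed item is met.

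**3. What the other routes add.** None of these depends on who committed the act.

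| Route | Reach |
|---|---|
| Family-violence AE category | The 7 days before the final assessment; which assessment is final is not stated |
| Therapist notification | Treatment delivery only |
| Questions on the three AE categories | Promised for posttreatment assessments |
| Review of participant data for safety concerns | No time limit, but no rule for classifying a victim's report |
| General SAE examples | No time limit, but someone must judge the event life-threatening or otherwise serious |

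The 7-day window is short. Against the 11 to 16 weeks that section 5.1D gives for treatment, one week is 1/16 = 6% to 1/11 = 9% of the course. Therapist notification covers much of the remainder while treatment lasts.

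**4. The 3-month survey.** Therapist notification has ended and the posttreatment questions have been asked. Under section 5.1K.1, provider review of IPV answers applies only while the therapy case is open, and never to SPs in standard PE. That leaves general data review, the general SAE examples and, if this survey counts as the final assessment, the 7-day category. The item list is the only remaining trigger specific to IPV, and it covers one direction.

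**5. Limit of the check.** The survey forms are in study materials that the documents do not include. Section 6.0 implies that the follow-up survey carries IPV items. Whether each act is asked in both directions cannot be seen.

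**The case against.** The strongest reply is that section 6.0 should be read as a whole. The sentence that sets the survey rule does not mention actor or target, and a survey report of IPV naturally includes a victim's report. The list is introduced as something the rule includes, so it may not be exhaustive. The seven phrases may be short labels for acts on a questionnaire that asks in both directions. The SAE sentence is presented as a consequence of the general examples, and nothing makes it the only way to an SAE.

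Much of this stands. A reader might infer that a victim's report cannot become an AE or SAE, or that such events would never reach the PI, the Central IRB or the DSMB. The documents do not support that: the routes in the second table above are open to violence in either direction, and section 6.0 passes events from the site PI to the study PI and on to the Central IRB. A reader might also want an estimate of the share of events missed. The documents give no disclosure rates for either member of a dyad, so any such figure would be invention.

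The reply does not remove the gap. A non-exhaustive list may widen what is reportable, but it does not widen an SAE rule that names items 6 and 7. If the form does have paired items, section 6.0 leaves the received half unclassified. If it does not, the expectation of victims' reports in section 5.1K.1 has no severe-violence items behind it.

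**Conclusion.** The point holds as a gap in the stated survey trigger. All 7 listed acts, and both acts that define an SAE, are worded for violence committed; none covers violence received. Sections 5.1K.1 and 5.3 expect reports from victims, so the three places need to be reconciled. The gap is partly filled during treatment and at posttreatment and is widest at the 3-month follow-up survey.

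The conclusion rests on a literal reading of the list and on the follow-up survey carrying IPV items, as section 6.0 implies. It does not depend on any rate of disclosure, and it is not a demonstration that victims' reports would be excluded in practice. It is a modest improvement to safety ascertainment that costs little.

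**What to change.** In section 6.0, state that endorsement of any of the seven acts on a posttreatment or follow-up survey, whether done by or done to the respondent and by either dyad member, is an AE. State also that item 6 or 7 in either direction is an SAE. Refer to sections 5.1K.1 and 5.3 so that the three places agree, and carry the wording into the AE form. Confirm that the survey asks each act in both directions; if it does not, the matching items are needed for the rule to work.

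Both members may report the same event, so check for duplicates within dyads. Do this at the coordinating level and without disclosing one member's report to the other, in keeping with the confidentiality concerns in section 5.1K.1. The change concerns classification and reporting only and leaves the outreach rules in that section as they are.

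The cost is one or two sentences, a few more AE and SAE reports, and the duplicate check.

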2.0 Introduction

Post-traumatic stress disorder (PTSD) occurs in as many as 1 in 5 combat Veterans¹⁵⁻¹⁷ and is associated with a host of negative, long-term consequences, including high rates of suicide and traumatic death.^{47,48} Trauma-focused cognitive-behavioral therapies for PTSD, like Prolonged Exposure Therapy (PE), result in significant improvement for many patients.²² While these proven psychotherapies have been disseminated in VA, poor adherence interferes with treatment response.^{49,50} Previous reviews of treatment completion in randomized controlled trials find that one in five patients dropout from active, change-focused treatments for PTSD, including PE and Cognitive Processing Therapy (CPT).²⁶ Rates of PE/CPT drop out are even higher

among Veterans,^{27-29;50;51} with estimates across studies converging around 35%.²⁷⁻²⁹ Importantly, those with the greatest need for PTSD treatment are likely at the highest risk for premature termination.²³ Similar problems with tolerating treatment are found among cognitive behavioral therapies, broadly.²⁶ Consequently, adherence, in and of itself, was identified as a top priority for real-world use of Evidence-Based Practices (EBPs) by the World Health Organization, Institute of Medicine, and the US Surgeon General.^{22;32-34}

PE addresses PTSD through confronting trauma memories to reduce fear, facilitate emotional processing, and promote new learning.⁵² Disrupting entrenched patterns of avoiding trauma reminders requires persistence by Veterans, through daily trauma exposure exercises at home. While these exercises require considerable Veteran commitment, they are similar to those of other demonstrated, effective, cognitive-behavioral therapies,⁵³ and psychotherapies with homework are associated with better treatment outcomes.^{25;54} Meta-analysis indicates 24% more patients will improve just from adding homework to a given psychotherapy.⁵⁴ Across multiple meta-analyses, compliance with these assignments predicts treatment response.^{24;25;53;56;57} Additionally, adherence to more challenging homework assignments, like exposure

[figure not shown]

Figure 1. Conceptual Model Underlying Partner Supported PE

exercises, predicts treatment response better than adherence to less difficult exercises (i.e., readings, self-monitoring).⁵⁵ Ultimately, the key for optimizing Veterans' gains from PE likely lies with efforts to maximize Veterans' engagement, through

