5.5 Study Evaluations

5.5A. Quantitative Data Collection (Aim 1, Aim 2, Exploratory Aim).

Except where indicated, data collection for the IC and RCT phase is identical. Aim 1 outcome variables will be obtained from Medical Records (attendance) and Provider Report (homework compliance). Aim 2 outcomes will be obtained from Baseline (week 0) and Posttreatment (16 weeks post-session 1) assessments of PTSD symptom severity, depression severity, quality of life, and relationship functioning. Aim 3 outcomes will be obtained from qualitative sources. Our Exploratory Aim outcomes will be obtained from Baseline, Posttreatment, and brief Weekly self-reports from Veterans and SPs. See below for measures.

5.5A.1 Aim 1. Aim 1 outcomes will be measured with methods drawn from Project HomeFront and our prior work coding session notes for PE/CPT treatment completion.⁵¹ PE attendance will be counted from review of Medical Records. Participants will have 'completed' PE when providers record they have successfully completed PE in a final session note. Providers will also be asked to log patient attendance and indicate the dates of attended sessions, missed sessions, and cancelled/rescheduled sessions. Homework compliance will be captured through patient observation by providers (Provider Report). Rating items were adapted from those used with Exposure and Response Prevention Therapy for Obsessive Compulsive Disorder (also a cognitive-behavioral exposure therapy).⁹³ Providers will also report on rates SP-provider contact weekly.

5.5A.2 Aim 2. Clinical outcomes for Aim 2 will be assessed through multiple forms (i.e., self-report and structured clinical interview), consistent with gold-standard methodology used in prior RCTs of PE and CPT. Baseline and posttreatment paper-and-pencil questionnaires will be completed by participants in both the RCT and IC phase of the study. Some participants in the IC phase will also receive structured interviews to allow the study team to implement all study procedures prior to beginning the RCT. IC participants will receive in-treatment assessments before sessions 2a and 2b to contribute to the intensive coaching and feedback providers receive for these early cases.

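### Section 6.0 names death and hospitalization as serious, but no procedure looks for deaths or non-psychiatric admissions, so after therapy ends their detection depends on incidental contact

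*Combined protocol and SAP*

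**What the plan says.** Section 6.0 (Reporting) defines an adverse event broadly, as "any untoward medical occurrence in a patient or clinical investigation subject administered an intervention". Later in the section, in the paragraph on intimate partner violence (IPV), it states: "Examples of serious adverse effects, according to the FDA, include death, life-threatening adverse events, suicide attempts, and hospitalization".

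The collection rule is narrower: "We will collect the following safety information (adverse events) that occurred within 7 days leading up to the final assessment". Three items follow: suicide attempts, admissions limited to "Hospitalizations for mental health", and family violence. Both dedicated routes refer back to that list. For therapists: "Therapists will be instructed to notify study staff immediately when such events occur during treatment delivery". For participants: "Questions regarding the occurrence of each of these three events will be included in posttreatment assessments". The regular consultation calls also track these events.

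Other provisions bear on safety:
- Section 6.0 sends any serious event, once learned of, to the Central IRB within 5 business days. It also counts severe IPV endorsed on the posttreatment and follow-up surveys as reportable.
- Section 5.1M provides ongoing safety monitoring, logging of participants' calls, and at least annual reporting to a DSMB.
- Section 5.1K.1 records use of the suicide management protocol as an adverse event and has surveys screened for suicidal ideation.

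Section 5.5A.1 already opens each Veteran's chart for another purpose: "PE attendance will be counted from review of Medical Records".

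**The concern.** The introduction (section 2.0) links PTSD to "high rates of suicide and traumatic death". A two-arm trial in this population should be able to say, by arm, how many Veterans died and how many were admitted to hospital. The plan treats both as serious, but it solicits neither death nor a medical admission. The reporting duties begin only when someone has learned of the event, and reporting is not ascertainment.

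The gap is widest once the therapist is no longer in contact. After that, what reaches the study depends on who answers a call and whether an SP chooses to mention it. If that differs between arms, a tabulation of known events would partly reflect the chance of hearing about them.

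**Working it through.** **Step 1. Events against solicited routes.** This is a comparison of texts; the plan gives no figure to reproduce.

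| Event | Therapist notice (during treatment) | Posttreatment questions | Other solicited route |
|---|---|---|---|
| Death, any cause | No | No | None |
| Non-psychiatric hospitalization | No | No | None |
| Life-threatening event | Only if a listed event | Only if a listed event | Severe IPV survey items |
| Psychiatric hospitalization | Yes | Yes | None stated |
| Suicide attempt | Yes | Yes | Ideation screen on surveys; use of the suicide management protocol |
| Family violence | Yes | Yes | Severe IPV items, posttreatment and 3-month |

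The first two rows are empty. No section asks the SP about them or sets a vital-status or chart check. Chart review is specified for attendance only.

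**Step 2. The 7-day window.** Posttreatment falls 16 weeks after session 1 for dropouts and no later than 24 weeks for late completers (section 5.5A.2).
- 16 weeks = 112 days; 7 / 112 = 6.3%.
- 24 weeks = 168 days; 7 / 168 = 4.2%.

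Therapist notification covers the listed events outside that window, but only during treatment. Section 5.1K.1 closes a case when the Veteran quits or outreach is exhausted, while a dropout is assessed at week 16. At the 35% dropout the introduction cites for Veterans, 0.35 x 156 = 54.6. About 55 Veterans could therefore spend part of the period to posttreatment outside therapist reporting.

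**Step 3. Could incidental detection differ by arm?** In family supported PE, SPs attend early sessions and receive two check-in calls from the provider (sections 2.2B and 5.1D). In standard PE, family attendance is not solicited (5.1C), and study staff deal with SPs only remotely (5.4A). An SP who knows the provider may be likelier to tell them of a death or admission. The planned SP contacts come early in treatment, so a difference after therapy is plausible but not shown.

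**Step 4. Illustrative size.** Follow-up runs from session 1 to 3 months after posttreatment.
- Shortest: 16/52 + 0.25 = 0.56 years; x 156 = 87 person-years.
- Longest: 24/52 + 0.25 = 0.71 years; x 156 = 111 person-years.

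The documents give no event rates. Assume 0.5% to 1% per year for death and 5% to 15% per year for any hospitalization:
- Deaths: 87 x 0.005 = 0.4 to 111 x 0.01 = 1.1.
- Hospitalizations: 87 x 0.05 = 4 to 111 x 0.15 = 17.

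**The case against.** **The plan has more safety machinery than the three-item list.** This stands. Section 6.0 follows the Central IRB's reporting table, which is not among the documents, so what it requires for deaths cannot be judged here. Any serious event that becomes known is reportable. These are still reporting rules and do not say how anyone would learn of the event.

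**A reader might infer that a death after therapy would show up only as an unreturned survey, or could not be told from a refusal.** The documents do not support that. Posttreatment non-responders receive a postcard, second and third mailings and telephone reminders, and the same survey method is used again at 3 months (5.5A.3). A posttreatment interview has to be arranged (5.5A.2). The SP, who at entry has contact with the Veteran at least three times a week (Table 4), is surveyed separately. Any of these could bring a death to light, but none is described as ascertainment.

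**A reader might also infer that the posttreatment PCL-5 comparison would be biased by imputing scores for Veterans who died.** That is not a main harm. Completers fill in the posttreatment survey at the final session, so a later death does not remove it. Section 5.6B also plans complete-case and available-data analyses. With about one death or fewer, any effect is trivial.

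**The sentence naming death and hospitalization explains how IPV items are classified and is not a collection list.** This is correct, and counting missing items against it would over-read it. The mismatch does not depend on that sentence alone, because the section's own adverse-event definition is broader still.

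**A targeted list is proportionate in a practical trial where both arms receive PE.** This is a fair point. It supports a light remedy, and about one death cannot support a formal comparison between arms.

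**Conclusion.** The point holds as a gap in ascertainment. Section 6.0 solicits three event types, largely within 7 days of the final assessment or during treatment. Deaths and non-psychiatric hospitalizations are left to incidental contact once therapy ends, and that contact may differ by arm.

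This rests on the text and needs no assumed rate. The counts of about 0.4 to 1.1 deaths and 4 to 17 hospitalizations are illustrations under assumed rates. The figure of 55 Veterans assumes the cited dropout rate applies to this trial. Differential detection by arm is a reasoned possibility without direct evidence.

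The gap affects the completeness of the safety data. It does not affect the primary attendance analysis and has no material effect on the PCL-5 analysis. The change is worth making because it is cheap and makes ascertainment the same in both arms.

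**What to change.** 1. Add death from any cause and any inpatient hospitalization to the section 6.0 list, and state that the 7-day window does not apply to these two items.
2. For every randomised Veteran, check both in the VA record from randomisation to the 3-month follow-up date, as part of the chart review already done for attendance. Where attendance is counted before that date, the review has to be timed or completed so that it reaches it.
3. Tabulate both by arm, descriptively.
4. Code death as its own reason for a missing outcome, separate from refusal and loss of contact.

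The cost is revised wording in section 6.0 and a few more minutes per chart. Most of the added events will be unrelated to the intervention, and some admissions outside VA will still be missed.
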